9.1.6 Concomitant Medications

Concomitant medications will be managed by the treating oncologist and recorded at each study visit by the study coordinator.

9.1.7 Study Drug(s) Blinding

The Duke ICS Pharmacy will be responsible for the preparation of the Td and the saline used for the pre-conditioning done prior to the fourth vaccine. The unpulsed DCs used for pre-conditioning will be prepared in the DBTIP Laboratory and delivered to the ICS for the labeling and distribution of the blinded pre-conditioning drugs (i.e., Td, unpulsed DCs, and saline). Only those key personnel needed for the preparation and distribution of the pre-conditioning drugs will be unblinded (i.e., ICS pharmacy staff and DBTIP Lab study drug manufacturing personnel, as well as the statisticians). The patient and the remaining key personnel (including the PI and research nurses administering the pre-conditioning drugs) will be blinded to the pre-conditioning regimen. Emergency unblinding procedures are described in [13.3](#).

The administration of pre-conditioning agent (Td or unpulsed DCs) will be blinded for Groups I and II, however, the administration of the pre-conditioning agent (Td) and basiliximab for Group III will not be. Hence, patients and providers will know when a patient has been assigned to the third treatment group (please see randomization and blinding SOP [18.2](#) in appendices).

9.2 Rationale for Selection of Dose, Regimen, and Treatment Duration

In our previous randomized clinical trial of 12 patients with newly-diagnosed GBM, we evaluated the impact of vaccine site pre-conditioning with Td toxoid[[125](#)]. Patients randomized to Td showed increased dendritic cell migration bilaterally and significantly improved progression-free and overall survival. Furthermore, we observed a modest association between effective DC migration to VDLNs and clinical outcomes. Based on the small sample size of the initial study, we would like to conduct a validation study with Td pre-conditioning that is powered sufficiently to evaluate the impact of DC migration on clinical outcomes. For that reason, we will conduct this validation trial with identical Td formulation, doses, and DC vaccine treatment schedules as in the original study. The 4th vaccine is the first monthly vaccine and we believe that the influence of the skin preconditioning would be most isolated at that time. In the original study, Td was used based on our mouse studies which revealed a memory CD4 T cell response to tetanus and unpulsed DCs were used based on research[[126](#)] that showed injection of DCs 24 hours before DC vaccine increased migration. Therefore, 2 conditioning regimens were tested: Td versus unpulsed DCs with saline in the contralateral side as control.

9.3 Rationale for Correlative Studies

Please see Section [7.2](#) ¹¹¹Indium-labeling of Cells for in vivo Trafficking Studies.

9.4 Definition of Evaluable Subjects, On Study, and End of Study

Subjects evaluable for the analysis of the primary endpoints of DC migration will include all randomized patients in Groups I and II who receive the 4th DC vaccine. Survival analyses will include all randomized patients.

Once the patient signs an ICF, that subject will be considered “on study”. Rationale for taking patient off protocol treatment will be documented.

9.5 Early Study Termination

This study can be terminated at any time for any reason by the PI-sponsor. If this occurs, all subjects on study should be notified as soon as possible. Additional procedures and/or follow up should occur in accordance with Section 12.7. Section 12.6 describes procedures and process for prematurely withdrawn patients.

10 STUDY DRUG

10.1 Names, Classification, and Mechanism of Action

Tetanus-diphtheria toxoid (Td toxoid adsorbed).

Td is indicated for active booster immunization against tetanus, diphtheria, and pertussis as a single dose; substitute 1-time dose of Tdap for Td booster, then standardly boost with Td every 10 years. Please refer to section 7.2 on the use of Td in this protocol.

DC vaccine

Human *CMV* pp65-LAMP mRNA-pulsed autologous DCs is the name of the study drug given with every vaccine. The name of the study drug at vaccine #4 will be 1×10^6 autologous unpulsed DCs or 1 Lf Td toxoid (depending on randomization). This vaccination will then consist of administration of 2×10^7 *CMV* pp65-LAMP mRNA loaded mature DCs as described above except that these DCs will be labeled with ^{111}In ($50 \mu\text{Ci} / 5 \times 10^7$ DCs) (Nycomed-Amersham, Chicago, IL) prior to injection. The class of action for all study drugs is a biological with the exception of the tetanus toxoid, which is an antitoxin.

Leukapheresis and dendritic cell vaccine generation

At least two leukaphereses will be performed on each patient enrolled on this protocol. The leukapheresis will be used for DC generation and immunologic monitoring. All leukaphereses will be approximately a 4-hour leukapheresis. It is estimated that 10-12 L of blood will be processed during this leukapheresis. An additional 4-hour leukapheresis will be requested from patients with positive immunological responses to the therapy for additional immunologic monitoring studies or for patients who need additional DCs generated to ensure a total of 10 vaccines.

DCs will be generated from the first leukapheresis *in vitro* by 7-day culture with GM-CSF and IL-4. PBMC for *in vitro* generation of DCs will be obtained by leukapheresis at the Duke Apheresis Unit and transported to the Cell Processing facility. For patients without sufficient venous access for leukapheresis a temporary intravenous catheter may be inserted.

At the end of the 7 day incubation for generation of DC a sample of the media is taken for mycoplasma testing, the cells are then harvested and electroporated with pp65-LAMP mRNA. The DCs are placed in a flask with AIM V media GM-CSF + IL-4 + TNF- α + IL-6 + IL-1 β at 37°C, 5% CO₂ for 18-20 hours for maturation. The cells are washed twice with PBS and frozen at 2-4 x 10⁷ cells/mL in 90% autologous human AB serum (Valley Biomedical, Winchester, VA 22602), 10% DMSO and 5% glucose in a controlled-rate freezer at a rate of 1°C/minute.

The DCs are then stored until needed at -135°C. After freezing, an aliquot of cells is thawed for QA/QC. This testing will look at viability, (>70%) endotoxin content, (<5 E.U. /Kg B.W.) mycoplasma contamination (negative) and sterility testing for aerobic and anaerobic bacterial cultures (1 x 10⁶ DCs) and fungal cultures (1 x 10⁶ DCs).

For each vaccination, cells that have passed QA/QC will be rapidly thawed at 37°C, washed three times with PBS and counted. The cell concentration will be adjusted to 5 x 10⁷ cells/mL and DCs will be resuspended in preservative free saline and placed into a sterile tuberculin syringe with a 27 gauge needle.

For all DC preparations, including unlabeled DCs for vaccination and ¹¹¹In-labeled DCs, from the final preparation a sample of cells will be sent for Gram stain and endotoxin testing prior to administration. DC vaccination will not be given until endotoxin testing has been passed (< 5.0 E.U/Kg) and the Gram stain has been found to be negative. An aliquot of cells will also be sent for aerobic and anaerobic bacterial cultures (1 x 10⁶ DCs) and fungal cultures (1 x 10⁶ DCs).

In the event of a positive sterility or mycoplasma test, the Principal Investigator or his or her designee will notify the treating physician and the patient. The FDA and IRB will be notified within 15 calendar days. The patient will be asked to be evaluated by a physician within 24 hours. If the patient has or develops a temperature >38.5 °C or clinical evidence of infection at the injection site (drainage, erythema or edema) or systemically, the patient will have swabs taken from the injection sites (if possible), along with blood, urine and sputum (if possible) sent for bacterial, fungal, and mycoplasmal culture and sensitivity testing. The patient will be treated expectantly with antibiotics based on the sensitivities of the organisms identified from the immunization product, and an independent infectious disease consultation will be obtained to guide further therapy. Any remaining immunization samples will be sent for sent for bacterial, fungal, and mycoplasmal culture and sensitivity testing and endotoxin testing, and immunizations will proceed only if the patient fully recovers and subsequent samples are found to be sterile.

If the patient is determined to have progressive disease, the patient may be considered for eligibility on the INTERCEPT study (INTracerebral EGFR-vIII Chimeric Antigen Receptor Gene-Modified T Cells for PaTients with Recurrent GBM, Pro00083828). If the patient is determined to be eligible for the INTERCEPT study (Pro00083828), the cells extracted from

leukapheresis while they were on this study, ELEVATE, will be used to create the CAR T cells for administration in the INTERCEPT study.

Basiliximab

Because our Phase I study showed no difference between 20 and 40 mg of basiliximab in T_{Reg} depletion, patients will receive basiliximab 20 mg 7 days before vaccines # 1 and # 2 in the Infusion Center of the Duke Cancer Center.

A maximum tolerated dose of basiliximab has not been determined in brain cancer patients. During the course of clinical studies, basiliximab has been administered to adult renal transplantation patients in single doses of up to 60 mg, or in divided doses over 3-5 days of up to 120 mg, without any associated serious adverse events.

Basiliximab is contraindicated in patients with known hypersensitivity to basiliximab or any other component of the formulation.

Basiliximab functions as an IL-2 receptor antagonist by binding with high affinity ($K_a = 1 \times 10^{10} \text{ M}^{-1}$) to the alpha chain of the high affinity IL-2 receptor complex and inhibiting IL-2 binding. Basiliximab is specifically targeted against IL-2R α , which is selectively expressed on the surface of activated T-lymphocytes. This specific high affinity binding of basiliximab to IL-2R α competitively inhibits IL-2-mediated activation of lymphocytes, a critical pathway in the cellular immune response involved in allograft rejection. While in the circulation, basiliximab impairs the response of the immune system to antigenic challenges. Whether the ability to respond to repeated or ongoing challenges with those antigens returns to normal after basiliximab is cleared is unknown.

Single-dose and multiple-dose pharmacokinetic studies have been conducted in patients undergoing first kidney transplantation. Cumulative doses ranged from 15 mg up to 150 mg. Peak mean \pm SD serum concentration following intravenous infusion of 20 mg over 30 minutes is 7.1 ± 5.1 mg/L. There is a dose-proportional increase in C_{max} and AUC up to the highest tested single dose of 60 mg. The volume of distribution at steady state is 8.6 ± 4.1 L. The extent and degree of distribution to various body compartments have not been fully studied. The terminal half-life is 7.2 ± 3.2 days. Total body clearance is 41 ± 19 mL/h. No clinically relevant influence of body weight or gender on distribution volume or clearance has been observed in adult patients. Elimination half-life was not influenced by age (20-69 years), gender or race.

All patients will receive basiliximab mixed with 50-100 mLs of sterile 0.9% sodium chloride or dextrose 5% solution. Basiliximab solution will be administered in a peripheral or central vein over a 20-60-minute period. When mixing the solution, gently invert the bag in order to avoid foaming; do not shake. Infusion should be administered intravenously immediately after preparation. If it needs to be held longer, it should be refrigerated between 2° and 8°C (36° to 46°F) for up to 24 hours or at room temperature for 4 hours after which it should be discarded. Medications for the treatment of severe hypersensitivity reactions including anaphylaxis should be available for immediate use. Patients will be monitored for anaphylactic events for 1 hour. Please see drug fact sheet in the Appendix – Section 18.7.

10.2 Packaging and Labeling of Study Agents

- For *CMV* pp65-LAMP mRNA-pulsed DCs:
Name
MRN
DOB
Drug: pp65DCs
Lot #: Lot 001
Caution New Drug Limited By Federal Law To Investigational Use
- For autologous unpulsed DCs:
Name
MRN
DOB
Drug: unpulsed DCs (blinded to personnel administering drug)
Lot #: Lot 001
Caution New Drug Limited By Federal Law To Investigational Use
- For tetanus diphtheria toxoid used in pre-conditioning
Name
MRN
DOB
Drug: Td (blinded to personnel administering drug)
Lot #: Lot 001
- For *CMV* pp65-LAMP mRNA loaded mature DCs labeled with ^{111}In ($50 \mu\text{Ci} / 5 \times 10^7$ DCs)
Name
MRN
DOB
Drug: Radiolabeled pp65DCs
Lot #: Lot 001
Caution New Drug Limited By Federal Law To Investigational Use
- For basiliximab:
Name
MRN
DOB
Drug: basiliximab
Lot #: Lot 001
- **TdTM** (Tetanus diphtheria toxoid adsorbed); Stored at 4°C used as Td booster vaccine
Drug: Td
Lot #
Expiration Date

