
If the patient is determined to have progressive disease, the patient may be considered for eligibility on the INTERCEPT study (INTracerebral EGFR-vIII Chimeric Antigen Receptor Gene-Modified T Cells for PaTients with Recurrent GBM, Pro00083828). If the patient is determined to be eligible for the INTERCEPT study (Pro00083828), the cells extracted from leukapheresis while they were on this study, ELEVATE, will be used to create the CAR T cells for administration in the INTERCEPT study.

Group I Treatment Plan (DC Vaccinations with pre-conditioning with Unpulsed DCs prior to the 4th DC vaccine) Patients in Group I will receive 1 x 10⁶ autologous unpulsed DCs in saline administered to a single side of the groin, and 0.4 mLs of saline administered to the contralateral side one day prior to the fourth DC vaccine, which is always given bilaterally at the groin site. Patients will then receive ¹¹¹In-labeled DCs as the 4th vaccine to compare the effects of different

skin preparations on DC migration followed by SPECT/CT imaging immediately and at 1 and 2 days after injections.

Group II Treatment Plan (DC Vaccinations with pre-conditioning with Td prior to the 4th DC vaccine)

Patients in Group II will receive a single dose of Td toxoid (1 flocculation unit, Lf, in 0.4 mLs) administered to a single side of the groin, and 0.4 mLs of saline administered to the contralateral side one day prior to the fourth DC vaccine, which is always given bilaterally at the groin site. Patients will then receive ¹¹¹In-labeled DCs as the 4th vaccine to compare the effects of different skin preparations on DC migration followed by SPECT/CT imaging immediately and at 1 and 2 days after injection.

Group III Treatment Plan (DC Vaccinations with basiliximab infusions prior to 1st and 2nd DC vaccine with Td pre-conditioning prior to 4th DC vaccine)

Patients in Group III will receive the first 3 DC vaccines every 2 weeks same as Groups I and II only they will also receive basiliximab 20 mg I.V. 7 days before DC vaccine # 1 and 7 days before DC vaccine # 2. Prior to the 4th vaccine, patients will receive a single dose of Td toxoid (1 flocculation unit, Lf, in 0.4 mLs) administered to a single side of the groin, and 0.4 mLs of saline administered to the contralateral side one day prior to the fourth DC vaccine, which is always given bilaterally at the groin site. This group will not undergo migration studies.

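### Section 10.2 lists label contents for the two blinded pre-conditioning products that differ by arm, which conflicts with the double blind for Groups I and II

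*Combined protocol and SAP*

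**What the plan says.** Section 9.1.7 sets the blind: "The patient and the remaining key personnel (including the PI and research nurses administering the pre-conditioning drugs) will be blinded to the pre-conditioning regimen". The same section has the unblinded ICS pharmacy label and distribute the blinded agents, and refers to a randomization and blinding SOP. Section 18.2 says the SOPs are uploaded separately, so that document is not part of the supplied text. Section 15.1 describes assignment to the first two arms as double-blinded; Group III is open.

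Section 10.2 lists label contents product by product. The Group I pre-conditioning product has the line "Drug: unpulsed DCs (blinded to personnel administering drug" and also the line "Caution New Drug Limited By Federal Law To Investigational Use". The Group II product has the line "Drug: Td (blinded to personnel administering drug" and no caution line. Section 10.2 gives no common label, code or masked wording for the pair, and lists no label for the pre-conditioning saline.

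**The concern.** A label is one of the few things that blinded staff handle directly. If its contents depend on the arm, the person giving the injection can learn the allocation without any emergency unblinding.

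The outcomes most exposed are those that rest on judgement:

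- PFS is the key secondary endpoint (Section 15.6.1). Under Section 12.7.4, progression has to be separated from pseudoprogression and weighed against clinical deterioration. The supplied text does not mention blinded independent review.
- Adverse events are attributed to study drug on a five-level scale (Section 13.1). That attribution feeds the unacceptable-toxicity definition in Section 9.1.2, which itself refers to a blinded pre-conditioning agent.

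Overall survival counts deaths, so knowledge of the arm could reach it only indirectly, through later treatment choices.

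**Working it through.** The plan gives no figure to reproduce here. The check is a line-by-line comparison of the two label listings in Section 10.2.

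| Label line | Unpulsed DCs (Group I) | Pre-conditioning Td (Group II) | Same? |
|---|---|---|---|
| Name, MRN, DOB | present | present | yes |
| Drug | names unpulsed DCs, noted as blinded | names Td, noted as blinded | no |
| Lot | Lot 001 | Lot 001 | yes |
| Investigational-use caution | present | absent | no |

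**Step 1: the Drug line.** Each entry names its agent and adds a note that the administering staff are blinded to it. A label that prints the name cannot also hide it, so some masking must be intended. Section 10.2 does not say what replaces the name.

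**Step 2: the rest of the label.** The blinding note is attached to the Drug line only. With that line fully masked, the two labels still differ by exactly one line, the caution statement.

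**Step 3: is the missing line accidental?** Across all products in Section 10.2, the caution line appears on the three cell products (pp65 DCs, unpulsed DCs, radiolabeled pp65 DCs) and on none of the other three (pre-conditioning Td, basiliximab, Td booster). It therefore follows product type, and a dropped line in the text is an unlikely explanation. Staff who give the labeled pp65 vaccines at vaccinations #1 to #3 would already have seen the line on a cell product.

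**Step 4: who is affected.** Randomization takes place at the post-RT visit, before vaccine #1 (Section 9.1). Pre-conditioning is given the day before vaccine #4 (Table 4). Only Group I and II patients who reach that visit receive one of these syringes. The target is 35 per arm (Section 15.9), so the ceiling is 35 + 35 = 70. Enrollment closed in April 2018 and the documents do not state how many reached the visit. Any randomized patient who progresses or withdraws earlier is not exposed to the labels.

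**The case against.** The strongest reply is that Section 10.2 may be a list of product identities and not the finished bedside label. The caution line follows product type, the Drug lines are already marked as blinded, and an unblinded pharmacy applies the labels under an SOP that may well specify a masked presentation. This stands as far as it goes: the documents do not show that anyone was unblinded. It does not remove the conflict. If the SOP prescribes a common masked label, Section 10.2 contradicts it. If the SOP follows Section 10.2, the labels differ by arm. The text needs correcting in either case.

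A second reply is that the consequences are limited. Section 12.7.4 asks for histological documentation of progression unless contraindicated, which restricts subjective calls. The steroid rule for removal in Section 12.6.1 applies at the first vaccination, before any blinded syringe is given. Both points are fair, and they confine the risk to the remaining judgements on progression and to adverse-event attribution.

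A third reply is that the matter is late. Taking the outer limit of 6 weeks from surgery to RT, then 6 weeks of RT, 4 weeks to the post-RT cycle, day 49 for vaccine #3 and day 21 of the next cycle gives 6 + 6 + 4 + 7 + 3 = 26 weeks, plus any gap before that cycle. The current version is dated November 2018, about seven months after enrollment closed. Few patients, if any, would still receive a new label. That stands, and it moves the weight of the fix to documentation and reporting.

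A reader might also infer that the syringes differ visibly in volume. Section 9.1 gives 0.4 mL for Td and for the contralateral saline in both groups, but no volume for the unpulsed DCs, and the vaccine concentration of 5 x 10^7 cells/mL in Section 10.1 would imply a much smaller injection. The documents do not support this. That concentration is stated for vaccinations and not for the pre-conditioning dose, and Section 10.1 also gives a different concentration for freezing. The Group I text, "autologous unpulsed DCs in saline administered to a single side of the groin, and 0.4 mLs of saline administered to the contralateral side", is compatible with equal volumes. A missing volume is missing detail and is not evidence of a mismatch.

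**Conclusion.** The point holds as an inconsistency in the plan's text that puts the blind at risk. Section 10.2 gives the two blinded products label contents that differ by arm in two lines, and one of these, the caution line, would survive masking of the agent name. Followed as written, the labels could identify the arm to the nurse or PI, whom Section 9.1.7 requires to be blinded.

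The risk is mainly to investigator-judged PFS and adverse-event attribution. It applies only to Group I and II patients who reach the pre-conditioning visit. A reader might infer that the arm was revealed for every patient, or that the primary survival comparison is compromised. The documents support neither: the SOP governing the syringes is not available, patients who leave early never receive one, and death is not a judged endpoint. No sample size, power or significance level changes.

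The conclusion assumes that Section 10.2 describes what is printed on the dispensed product, which is its plain reading but which only the SOP or pharmacy records can confirm.

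**What to change.** - In Section 10.2, specify one identical coded label for both blinded pre-conditioning products: the same lines, the same caution statement and no agent name.
- Confirm against the randomization and blinding SOP that the syringes match in label, volume and appearance, and say so in Section 9.1.7.
- For patients already pre-conditioned, document from pharmacy records which labels were used. If they were as listed in Section 10.2, qualify the double-blind description when PFS and safety are reported.

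The cost is a label template, a short text edit and a records check. Collected data and planned analyses are unchanged.

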10.3 Supply, Receipt, and Storage

The DCs will be stored in a locked liquid nitrogen freezer in the Molecular Products and Cellular Therapies (MPACT) cGMP facility. The Nautilus LIMS (Laboratory Information Management System) database will track receipt and storage location.

Table 2. Storage of Study Agents

MPACT Facility	Duke ICS Pharmacy	Duke Radiopharmacy
CMV pp65-LAMP mRNA-pulsed DCs	Td used for booster and for pre-conditioning	CMV pp65-LAMP mRNA loaded mature DCs labeled with ¹¹¹ In
Unpulsed DCs	Saline used for pre-conditioning	
	Basiliximab	

